7.1.2. Liver Injury

A participant who meets the criteria of potential DILI (Hy's law) case as described in Section [10.6](#) will be withdrawn from study intervention.

7.1.3. ECG Changes

A participant who meets either bulleted criterion based on ECG readings will be withdrawn from the study intervention.

- QTcF >500 ms.
- Change from baseline: QTcF \geq 60 ms.

If a clinically significant finding is identified (including, but not limited to, changes from baseline in QTcF after enrollment), the investigator or qualified designee will determine if the participant can continue in the study and if any change in participant management is needed. This review of the ECG printed at the time of collection must be documented. Any new clinically relevant finding should be reported as an AE.

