7. DISCONTINUATION OF STUDY INTERVENTION AND PARTICIPANT DISCONTINUATION/WITHDRAWAL

7.1. Discontinuation of Study Intervention

It may be necessary for a participant to permanently discontinue study intervention. Reasons where study intervention will be permanently discontinued include the following:

- AE of Grade 3 severity or greater and considered by the investigator to be related to the study intervention;
- SAE considered by the investigator to be related to the study intervention;
- Requirement for prohibited concomitant medication;
- Participant who becomes pregnant during the course of the study;
- Study terminated by the Sponsor;
- Withdrawal by participant or legally authorized representative;
- If post-screening eGFR falls to $<30 \text{ mL/min}/1.73 \text{ m}^2$ the participant will be instructed to discontinue any remaining study intervention doses as soon as study staff become aware of the eGFR results.
- If the participant is hospitalized, and none of the criteria above are met, study intervention may continue to be administered, as feasible, and based on the judgment of the investigator.

Discontinuation of study intervention does not represent withdrawal from the study. If study intervention is permanently discontinued, the participant should remain in the study to be evaluated for all subsequent planned assessments. See the [SoA](#) for data to be collected at the time of discontinuation of study intervention and follow-up for any further evaluations that need to be completed.

In the event of discontinuation of study intervention, it must be documented on the appropriate CRF/in the medical records whether the participant is discontinuing further receipt of study intervention or also from study procedures, further study follow-up, and/or future collection of additional information.

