7.1.4. Pregnancy

If a participant becomes aware of pregnancy during the study, they are to be discontinued from study intervention.

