7.1.5. COVID-19 (SARS-CoV-2) and influenza

Participants will be tested for SARS-CoV-2 and influenza within 7 days of study randomization. If a participant develops an infection from influenza or SARS-CoV-2 through the course of the study, the investigator will decide whether to continue or permanently discontinue treatment with the study drug. If the patient's treatment requires a prohibited medication (eg, nirmatrelvir/ritonavir), the study drug must be discontinued. If a participant has SARS-CoV-2 or influenza during the study, this should be reported as an AE or SAE (as appropriate).

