7.2. Participant Discontinuation/Withdrawal From the Study

A participant may withdraw from the study at any time at their own request. Reasons for discontinuation from the study include the following:

- Refused further study procedures;
- Lost to follow up;
- Study terminated by Sponsor;
- Withdrawal of consent by authorized legal representative.

At the time of discontinuing from the study, if possible, an early discontinuation visit should be conducted. See the [SoA](#) for assessments to be collected at the time of study discontinuation and follow-up and for any further evaluations that need to be completed.

If a participant withdraws from the study, they may request destruction of any remaining samples taken and not tested, and the investigator must document any such requests in the site study records and notify the sponsor accordingly.

If the participant withdraws from the study and also withdraws consent (see Section [7.2.1](#)) for disclosure of future information, no further evaluations will be performed and no additional data will be collected. The sponsor may retain and continue to use any data collected before such withdrawal of consent.

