7.2.1. Withdrawal of Consent

Participants who request to discontinue receipt of study intervention will remain in the study and must continue to be followed for protocol-specified follow-up procedures. The only exception to this is when a participant specifically withdraws consent for any further contact with them or persons previously authorized by the participant to provide this information. Participants should notify the investigator in writing of the decision to withdraw consent from future follow-up, whenever possible. The withdrawal of consent should be explained in detail in the medical records by the investigator, as to whether the withdrawal is only from further receipt of study intervention or also from study procedures and/or posttreatment study follow-up, and entered on the appropriate CRF page. In the event that vital status (whether the participant is alive or dead) is being measured, publicly available information should be used to determine vital status only as appropriately directed in accordance with local law.

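### Section 7.1.3 makes a post-randomization ECG finding a decision about staying in the study, whereas parent Section 7.1 stops only study drug and keeps follow-up

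*Protocol*

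**What the plan says.** Protocol Section 7.1.3 contains two rules. The first is numeric, with thresholds of QTcF above 500 ms or a change from baseline of at least 60 ms: "A participant who meets either bulleted criterion based on ECG readings will be withdrawn from the study intervention". The second covers any clinically significant ECG finding and expressly includes QTcF changes after enrollment. For those, "the investigator or qualified designee will determine if the participant can continue in the study", together with any change in management.

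The parent section, 7.1, separates stopping drug from leaving the study: "If study intervention is permanently discontinued, the participant should remain in the study to be evaluated for all subsequent planned assessments". The neighbouring rules keep to the drug:

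- Liver injury (7.1.2): the participant "will be withdrawn from study intervention".
- Pregnancy (7.1.4): "they are to be discontinued from study intervention".
- SARS-CoV-2 or influenza (7.1.5): "the investigator will decide whether to continue or permanently discontinue treatment with the study drug".

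Leaving the study has its own section, 7.2. Its listed reasons include neither an ECG finding nor an investigator decision.

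**The concern.** The second rule in 7.1.3 makes continued study participation, not continued dosing, the thing the investigator decides. Section 7.1 treats these as different things.

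The difference matters for the primary endpoint. Under Section 9.1.1.1 the estimand uses all available data whether or not the participant stays on treatment. Section 8.2.1 collects RSV-related hospitalizations at study visits. A participant removed on the investigator's decision has no later visits, so any later hospitalization may go unrecorded even though consent was never withdrawn. Section 9.3.2.2 would then fill the Day 28 status by multiple imputation. A follow-up outcome that could have been observed would be replaced by a modelled one.

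The people concerned may also not be typical. Section 8.2.1 allows cardiac decompensation in patients with underlying cardiac disease to count as RSV-related, and heart failure is a qualifying risk factor in Section 5.1. Someone with a new significant ECG finding could therefore differ in event risk. That is an inference, which the documents do not quantify.

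**Working it through.** No figure in the plan is at issue, so the main check is a comparison of the texts.

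**1. Does the rule reach randomized participants?** Yes. Section 7.1.3 names findings after enrollment, and Section 9.2 defines enrolled as consented and randomized. The pre-dose ECG is a separate matter: exclusion criterion 4 in Section 5.2 makes it an eligibility judgement, and Section 8.3.3 has the screening ECG interpreted before enrollment.

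**2. What is being decided?**

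| Protocol section | Trigger | What stops, or may stop |
|---|---|---|
| 7.1.3, first rule | QTcF threshold | study intervention |
| 7.1.3, second rule | any clinically significant ECG finding | participation in the study |
| 7.1.2 | potential Hy's law case | study intervention |
| 7.1.4 | pregnancy | study intervention |
| 7.1.5 | SARS-CoV-2 or influenza | study drug |

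Only the second ECG rule goes beyond the drug. Section 7.1.5 is the closest comparison. It gives the investigator the same kind of discretion but confines it to treatment.

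**3. Can the study be read as the study drug?** Only during dosing. Under Section 6.1.1 dosing ends on Day 5, or on Day 6 if one dose was taken on Day 1. The Schedule of Activities allows ECGs after screening as needed and sets no end date. For a finding after dosing ends there is no drug left to continue, so the decision could concern only participation.

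**4. What would be lost?** Not everything. Section 7.2 asks for an early discontinuation visit where possible. The Schedule of Activities has that visit record RSV-related visits, admissions and survival status. Section 8.2.2 lets deaths come from registries and other sources. The exposure is therefore RSV-related hospitalization after exit and up to Day 28.

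**5. Scale per participant.** With 1:1 randomization and n participants analysed per arm, one lost status can move that arm's proportion by at most 1/n.

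- All 2375 planned participants analysed: n = 2375/2 = 1187.5, and 1/1187.5 = 0.084 percentage points.
- 80% analysed (an assumption, because the analysed number is blacked out): n = 0.8 × 1187.5 = 950, and 1/950 = 0.105 percentage points.

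This bounds the effect of one participant. It says nothing about how many there would be.

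**The case against.** The strongest reply is that this is loose drafting which the structure already resolves. Section 7.1.3 sits under a heading about discontinuing study intervention, the parent text keeps such participants in follow-up, and departure from the study is handled in 7.2. Section 7.1.3 asks for a determination and orders nobody out. If someone did leave, study discontinuation is a named intercurrent event and imputation was planned.

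Much of this stands. The intended reading is clear, and 7.1 points to it. Two things remain. The drug-only reading fails once dosing has ended. And planning to impute a missing outcome is no reason to permit the loss of one that could be observed.

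A reader might infer more than the documents support:

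- **A conflict with 7.2.1.** Its consent rule is strict ("The only exception to this is when a participant specifically withdraws consent for any further contact with them"), but it is written for participants who themselves ask to stop drug. An investigator's ECG decision is not such a request.
- **A breach of 7.2.** That list opens with "Reasons for discontinuation from the study include the following", so it is not closed.
- **A contradiction with 7.1.2, 7.1.4 and 7.1.5.** These govern other triggers. They show the drafting pattern and do not conflict with 7.1.3.
- **The same fault in Appendix 9 (Section 10.9)**, where the investigator judges ongoing participation after prohibited medication. Section 7.1 largely answers this: it lists the need for such medication as a reason to stop study intervention and then keeps the participant in the study.

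**Conclusion.** The point holds as a direct tension between the second rule of 7.1.3 and its parent, 7.1, for findings after randomization. It is minor. Read literally, the text permits avoidable loss of later hospitalization status in participants who have not withdrawn consent.

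The number affected is probably very small, because the only scheduled ECG is at screening. The documents give no basis for a count. A reader might try to judge frequency from the days remaining after each visit, or from the Section 2.2.4 statement on QTcF changes in Study C5241001. Neither measures it: no ECG is scheduled at the later visits, and the second rule covers any clinically significant finding rather than a QTcF threshold. No bias or type I error figure follows either.

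The conclusion concerns the plan as designed. SAP Section 2.1 records that the study was discontinued for business reasons with very few participants. SAP version 2 has no inferential testing (Section 5.1) and removed multiple imputation (Section 1), so the reported results would not materially change.

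**What to change.** In Protocol Section 7.1.3, for findings after randomization, replace the decision about continuing in the study with one about whether the participant *can continue study intervention*. Keep the existing words on participant management. Then add: *Follow-up continues as in Section 7.1 unless consent for further contact is withdrawn.* That sentence also covers findings after the last dose. State that the pre-dose ECG remains an eligibility decision under exclusion criterion 4.

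The cost is a few words in one section. No visit or procedure is added, since the visits are already in the Schedule of Activities, and the investigator keeps full discretion over dosing and care. Because the study has been discontinued, the change is for any reuse of this text.

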7.1.4. Pregnancy

If a participant becomes aware of pregnancy during the study, they are to be discontinued from study intervention.

7.1.5. COVID-19 (SARS-CoV-2) and influenza

Participants will be tested for SARS-CoV-2 and influenza within 7 days of study randomization. If a participant develops an infection from influenza or SARS-CoV-2 through the course of the study, the investigator will decide whether to continue or permanently discontinue treatment with the study drug. If the patient's treatment requires a prohibited medication (eg, nirmatrelvir/ritonavir), the study drug must be discontinued. If a participant has SARS-CoV-2 or influenza during the study, this should be reported as an AE or SAE (as appropriate).

7.1.6. Temporary Discontinuation

Not permitted.

7.1.7. Rechallenge

Not permitted.

7.2. Participant Discontinuation/Withdrawal From the Study

A participant may withdraw from the study at any time at their own request. Reasons for discontinuation from the study include the following:

- Refused further study procedures;
- Lost to follow up;
- Study terminated by Sponsor;
- Withdrawal of consent by authorized legal representative.

At the time of discontinuing from the study, if possible, an early discontinuation visit should be conducted. See the [SoA](#) for assessments to be collected at the time of study discontinuation and follow-up and for any further evaluations that need to be completed.

If a participant withdraws from the study, they may request destruction of any remaining samples taken and not tested, and the investigator must document any such requests in the site study records and notify the sponsor accordingly.

If the participant withdraws from the study and also withdraws consent (see Section [7.2.1](#)) for disclosure of future information, no further evaluations will be performed and no additional data will be collected. The sponsor may retain and continue to use any data collected before such withdrawal of consent.

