8.1.2. Telehealth Visits

Telehealth visits may be used to assess participant safety and collect data points. Telehealth includes the exchange of healthcare information and services via telecommunication technologies (eg, audio, video, videoconferencing software) remotely, allowing the participant and the investigator to communicate on aspects of clinical care, including medical advice, reminders, education, and safety monitoring. Assessments that may be performed during a telehealth visit are described in the [SoA](#).

Study participants must be reminded to promptly notify site staff about any change in their health status.

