8.2.2. Survival status

Information about the death of a participant may be collected from death registries, hospital databases, other healthcare professionals, from participant's legal representatives, or other persons authorized by the participant and according to local regulations. The death of a participant cannot be assumed by their non-responsiveness, as the participant may be lost to follow-up.

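### Protocol 7.2 treats refusal of procedures as leaving the study, and no contact is scheduled afterwards, so RSV-related hospitalization goes uncollected for leavers who could still be reached.

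*Protocol*

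**What the plan says.** Protocol 7.1 has the site record "whether the participant is discontinuing further receipt of study intervention or also from study procedures, further study follow-up, and/or future collection of additional information". It therefore recognizes several degrees of stopping, and it keeps a participant who stops drug in the study for the remaining planned assessments.

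Section 7.2.1 says "Participants who request to discontinue receipt of study intervention will remain in the study" and are to be followed. It adds: "The only exception to this is when a participant specifically withdraws consent for any further contact with them". The investigator is to document "whether the withdrawal is only from further receipt of study intervention or also from study procedures and/or posttreatment study follow-up".

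Section 7.2 lists reasons for discontinuation from the study itself, and one of them is "Refused further study procedures". On leaving, if possible, "an early discontinuation visit should be conducted". The section points to the SoA for anything further. It ends data collection only when the participant both leaves and withdraws consent for future information.

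Two other provisions bear on collecting outcomes without a visit. Section 8.1.2: "Telehealth visits may be used to assess participant safety and collect data points". Section 8.2.2: "Information about the death of a participant may be collected from death registries, hospital databases, other healthcare professionals".

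**The concern.** Section 7.2 does not use the distinctions that 7.1 and 7.2.1 ask sites to record. A participant who has had enough of swabs and clinic visits, but would answer the telephone, can be closed out after a single early discontinuation visit.

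The primary endpoint is an RSV-related acute-care stay of at least 24 hours, or death from any cause, through Day 28. It needs no swab, blood sample or clinic attendance and can be asked about by telephone. The primary estimand (9.1.1.1) handles discontinuation from the study by using all available data regardless of it. If nothing is collected after leaving, that strategy has little to work with and the result rests on imputation. People who leave because they feel too ill to attend, or do not tolerate the tablets, may differ in outcome or by arm. Missingness of that kind is where an imputation model is least secure.

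**Working it through.** The check is mainly textual.

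**1. Which participants fall under conflicting text?**
- Stops drug, refuses procedures, accepts contact: 7.2 allows discontinuation from the study; 7.2.1 requires continued follow-up. This is a direct conflict.
- Refuses procedures without stopping drug, accepts contact: 7.2 applies, but 7.2.1 is written for people stopping drug. This is an ambiguity.
- Withdraws consent for contact: both sections agree that follow-up ends. There is no issue.

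**2. What is collected after the early discontinuation visit?**
- SoA: the early discontinuation column includes RSV-related visits and admissions, and survival status. No column, row or note provides a later contact, although 7.2 sends the reader there.
- 8.2.1: details of RSV-related hospitalization are gathered at study visits.
- 8.2.2: outside sources are allowed for death only.
- 8.1.2: telehealth is permitted in general, but the section refers to the SoA for which assessments, and the published SoA marks none. The schema has a Day 35 telephone contact, for participants still in the study.
- 7.3: contact attempts are required before someone is called lost to follow-up. A reachable refuser is not lost, and no outcome call is required.

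So death through Day 28 and admissions up to the early discontinuation visit can be captured. RSV-related hospitalization after that visit is not scheduled to be collected.

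**3. How is the gap handled in analysis?**
- Protocol 9.3.2.2: multiple imputation of event status for those who leave before Day 28 without an event.
- SAP version 2: imputation and inference were removed because the study stopped with very few participants. SAP 6.1.1.1 does not say how a leaver with unknown Day 28 status enters the primary proportion. For hospital-free days, SAP 6.2.1.1.5.1 counts a leaver who is out of hospital on the discontinuation date as hospital-free to Day 28, so a later unrecorded admission would become a good outcome.

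**4. Size.** The planned total of about 2375 cannot be reproduced, because the event rate, treatment difference and inflation factors are redacted; the point does not rest on it. The effect on power can be illustrated without an event rate. Let d be the share with a missing Day 28 outcome (assumed; the documents give no readable value). With one-sided alpha 2.5%, 90% power, a fixed design and no allowance for loss:

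power = Φ[(1.960 + 1.282) × √(1 − d) − 1.960]

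| d | participants out of 2375 | power | total needed to offset, 2375/(1 − d) |
|---|---|---|---|
| 1% | 24 | 89.7% | 2399 |
| 2% | 48 | 89.4% | 2424 |
| 3% | 71 | 89.1% | 2449 |
| 5% | 119 | 88.5% | 2500 |
| 10% | 238 | 86.8% | 2639 |

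The loss is 0.3 to 3.2 points over this range. One of the redacted inflation steps may already cover it, and d includes people whom a telephone call would not recover.

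**The case against.** The strongest reply is that 7.2 only lists reasons that may apply when someone chooses to leave; it does not tell sites to close out a participant who declines a swab. Refusal of procedures is also the only entry that a competent participant initiates, since the consent entry concerns a legal representative, so it probably serves as the voluntary-withdrawal category. That part stands: the entry should be clarified rather than deleted.

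A second reply is that collection does not end on leaving. Section 8.4.1 runs active adverse event collection through Day 35 unless consent for future information is withdrawn, and inpatient hospitalization is a seriousness criterion (10.3.2). This helps only in part. The same section says investigators need not actively seek events once participation has concluded, and 10.3.1 excludes expected progression of the studied disease unless it is more severe than expected. The admissions that make up the primary endpoint could therefore be missed.

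A reader might infer more than the documents support, in three ways:
- *That the primary outcome is lost.* It is not. Deaths and admissions up to the early discontinuation visit count, and the protocol planned imputation for the rest.
- *That SAP version 2 chose to ignore missing outcomes.* It dropped imputation because the trial stopped early, and it makes no test.
- *That a number of lost events can be given.* Assuming that 3% to 8% of 2375 leave while reachable, at 5% to 15% event risk, gives 71 × 5% = 3.6 up to 190 × 15% = 28.5 events. The documents supply none of these rates. The primary set is mITT-infected, not all randomized, and events before leaving are already captured. Nor can 28.5 events at 15% risk be set against 2375 × 5% = 119; at 15% the comparator is 356.

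**Conclusion.** The point holds as a gap in the plan as designed. Section 7.2 does not separate refusing procedures from refusing contact. It conflicts with 7.2.1 for participants who also stop drug and is ambiguous for the others. After the early discontinuation visit, the hospitalization component of the primary endpoint has no scheduled collection for leavers who still accept contact, so for them the estimand would rest on imputation.

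The size of any bias cannot be derived from the documents, and the power figures above are illustrations under an assumed missing share. I regard bias as the larger worry: a sample size allowance can restore precision but does not correct missingness related to outcome or arm. No hypothesis test is affected now, because SAP version 2 is descriptive only. This is a worthwhile, inexpensive improvement, not a flaw that invalidates the design.

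**What to change.** - **Section 7.2:** keep a voluntary-withdrawal category, but state that refusing procedures ends procedures only and that follow-up ends only when consent for contact is withdrawn. This aligns it with 7.1 and 7.2.1.
- **SoA:** add one Day 28 telephone or telehealth contact, recording RSV-related hospitalization and vital status, for everyone who leaves visits without withdrawing that consent. Section 8.1.2 already permits the route in general.
- **Section 8.2.2:** extend the permitted outside sources to RSV-related hospitalization where local rules allow.

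The cost is amendment wording and one call for each participant concerned: a small added site burden, with no new procedure or staff.
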